6.1.3. Primary Safety Endpoints: Maternal Participants

6.1.3.1. Local Reactions Within 7 Days After Vaccination

- Analysis set: Safety – maternal ([Section 4](#)).
- Analysis methodology: Descriptive summary statistics.
- Intercurrent events and missing data: For participants who discontinue, all collected data will be included; intermediate missing values will not be imputed.
- For each group, n, percentage, and 95% CI will be presented by vaccine group for the following variables (additional variables might be added depending on team's decision):
 - Presence or absence of any local reaction on each day (Days 1-7) after vaccination.
 - Presence or absence of any local reaction on “any day (Day 1-7)” after vaccination.
 - Maximum severity of each local reaction on “any day (Day 1-7)” after vaccination.
- For each group, n, mean, median, minimum, and maximum will be presented by vaccine group for the following variables:
 - Duration of each local reaction after vaccination.
 - Onset day of each local reaction after vaccination.
 - Onset day of any local reaction after vaccination.

6.1.3.2. Systemic Events Within 7 Days After Vaccination

- Analysis set: Safety – maternal ([Section 4](#)).
- Analysis methodology: Descriptive summary statistics.
- Intercurrent events and missing data: For participants who discontinue, all collected data will be included; intermediate missing values will not be imputed.

- For each group, n, percentage, and 95% CI will be presented by vaccine group for the following variables (additional variables might be added depending on team's decision):
 - Presence or absence of any systemic event on each day (Days 1-7) after vaccination.
 - Presence or absence of any systemic event on "any day (Day 1-7)" after vaccination.
 - Maximum severity of each systemic event on "any day (Day 1-7)" after vaccination.
- For each group, n, mean, median, minimum, and maximum will be presented by vaccine group for the following variables:
 - Duration of each systemic event after vaccination.
 - Onset day of each systemic event after vaccination.
 - Onset day of any systemic event after vaccination.

6.1.3.3. AEs Within 1 Month After Vaccination

- Analysis set: Safety – maternal ([Section 4](#)).
- Analysis methodology: Descriptive summary statistics for Tier 3 events; difference and 95% CI between the vaccine group and the placebo group for Tier 2 events. No Tier 1 events are identified.
- Intercurrent events and missing data: For participants who discontinue, all collected data will be included; missing AE dates will be imputed as described in Pfizer's Vaccine Statistics Rulebook.
- For each group, the number of participants with AEs within 1 month (30 days) after vaccination (n), percentage, and 95% CI will be presented for any AE, each SOC, and each PT within each SOC, by vaccine group. For AEs classified as Tier 2 events, the difference in proportions and associated 2-sided 95% CI between the vaccine group and the placebo group will be presented.

6.1.3.4. SAEs Throughout the Study

- Analysis set: Safety – maternal ([Section 4](#)).
- Analysis methodology: Descriptive summary statistics.
- Intercurrent events and missing data: For participants who discontinue, all collected data will be included; missing AE dates will be imputed as described in Pfizer's Vaccine Statistics Rulebook.

- For each group, the number of participants with SAEs throughout the study (n), percentage, and 95% CI will be presented for any event, each SOC, and each PT within each SOC, by vaccine group.

6.2. Secondary Endpoints

6.2.1. Secondary Efficacy Endpoints – Infant Participants

6.2.1.1. Hospitalization Due to RSV (as Confirmed by the EAC) Occurring Within 90 Days, 120 Days, 150 Days, 180 Days, and 360 Days After Birth

6.2.1.1.1. Main Analysis

- Estimand strategy: Hypothetical.
- Analysis set: Evaluable efficacy – infant ([Section 4](#)).
- Analysis methodology: VE will be analyzed using a conditional exact test based on the binomial distribution of the number of disease cases in the RSV vaccine group, given the total number of cases in both groups.
- Intercurrent events and missing data: All postdiscontinuation or postviolation observations will be censored; such events include the infant receiving palivizumab or another monoclonal antibody targeting RSV and the infant receiving transfusions of more than 20 mL/kg of any blood products at \leq 180 days of age. For each group, the number (n), percentage, and 95% CI of cases of hospitalization due to RSV occurring within 90 days, 120 days, 150 days, 180 days, and 360 days after birth as confirmed by the EAC will be presented.
- VE compared to placebo along with the 95% CI will be presented. This will be based on raw numbers of cases and also with an adjustment for any differences in follow-up time. The analyses up to 120 days, 150 days, 180 days, and 360 days will be performed if previous analysis for each interval meets the efficacy criteria.
- Kaplan-Meier curves showing accrual of cases for this endpoint over 360 days will be presented.

6.2.1.1.2. Supplementary Analysis

The main analysis will also be performed based on the mITT efficacy infant population. In addition, an analysis including only hospitalization cases that also had ICU admission will be conducted in the evaluable for efficacy population.

6.2.1.2. MA-LRTI Due to Any Cause With Protocol-Defined Criteria Occurring Within 90 Days, 120 Days, 150 Days, 180 Days, and 360 Days After Birth

All attributes (including analysis methodology and reporting results) for this endpoint will be similar to those stated in Section 6.2.1.1.

6.2.1.3. RSV-Positive MA-LRTI Occurring Within 210 Days, 240 Days, 270 Days, and 360 Days After Birth

6.2.1.3.1. Main Analysis

- Estimand strategy: Hypothetical.
- Analysis set: Evaluable efficacy – infant ([Section 4](#)).
- Analysis methodology: VE will be analyzed using a conditional exact test based on the binomial distribution of the number of disease cases in the RSV vaccine group, given the total number of cases in both groups.
- Intercurrent events and missing data: All postdiscontinuation or postviolation observations will be censored; such events include the infant receiving palivizumab or another monoclonal antibody targeting RSV and the infant receiving transfusions of more than 20 mL/kg of any blood products at \leq 180 days of age. For each group, the number (n), percentage, and 95% CI of RSV-positive MA-LRTI cases occurring within 210 days, 240 days, 270 days, and 360 days after birth will be presented.
- VE compared to placebo along with the 95% CI will be presented. This will be based on raw numbers of cases and also with an adjustment for any differences in follow-up time. The analyses up to 240 days, 270 days, and 360 days will be performed if previous analysis for each interval meets the efficacy criteria.
- Kaplan-Meier curves showing accrual of cases for this endpoint over 360 days will be presented.

6.3. Other Endpoints

6.3.1. Exploratory Endpoints: Infant Participants

6.3.1.1. RSV-Positive MA-RTI (as Confirmed by the EAC) Occurring Within 90 Days, 120 Days, 150 Days, and 180 Days After Birth

- Analysis set: Evaluable efficacy – infant ([Section 4](#)).
- Analysis methodology: VE will be analyzed using a conditional exact test based on the binomial distribution of the number of disease cases in the RSV vaccine group, given the total number of cases in both groups. Events that happen after the infant received palivizumab or another monoclonal antibody targeting RSV or after he/she had transfusions of more than 20 mL/kg of any blood products at \leq 180 days of age will be excluded. For each group, the number (n), percentage, and 95% CI of RSV-positive MA-RTI cases occurring within 90 days, 120 days, 150 days, and 180 days after birth will be presented for each group.
- VE compared to placebo along with the 95% CI will be presented. The analyses up to 120 days, 150 days, and 180 days will be performed if previous analysis for each interval meets the efficacy criteria.

- Kaplan-Meier curves showing accrual of cases for this endpoint over 180 days will be presented.

6.3.1.2. RSV-Positive MA-RTI Occurring 181 to 730 Days After Birth

- Analysis set: Evaluable efficacy – infant ([Section 4](#)).
- Analysis methodology: VE will be analyzed using a conditional exact test based on the binomial distribution of the number of disease cases in the RSV vaccine group, given the total number of cases in both groups. Events that happen after the infant received palivizumab or another monoclonal antibody targeting RSV or after he/she had transfusions of more than 20 mL/kg of any blood products at ≤ 180 days of age will be excluded.
- For each group, the number (n), percentage, and 95% CI of RSV-positive MA-RTI cases occurring within 181 to 730 days will be presented for each group.
- For each group, the number (n), percentage, and 95% CI of RSV-positive MA-RTI cases occurring within 361 to 730 days will be presented for each group (just for the participants enrolled in the first year of the study).
- VE compared to placebo along with the 95% CI will be presented for each analysis interval separately.

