2.2. Study Design

This is a Phase 3, multicenter, randomized, double-blinded, placebo-controlled study to assess the efficacy, safety, and immunogenicity of bivalent RSVpreF or placebo (1:1 randomization) in infants born to healthy women vaccinated during pregnancy, and the safety and immunogenicity in the pregnant women. This will be a global study, including sites in both the northern and southern hemispheres, and it will span multiple RSV seasons.

This is an event-driven study with a target of 124 adjudicated (primary-endpoint) cases of MA-LRTI due to RSV (meeting the case definition in the per-protocol infant population described in [Section 9.2 of the protocol](#)). Vaccination of maternal participants will occur at a time of year such that the infant is likely to be exposed to seasonal RSV during the first 6 months of life. It was anticipated that approximately 6900 mother-infant pairs would be needed to accumulate 124 per-protocol cases prior to the global COVID-19 pandemic. With the variable RSV season, the sample size may need to be increased and enrollment could go up to 10,000 maternal participants based on the number of RSV cases.

Study-eligible pregnant women will be randomized in a 1:1 ratio to receive a single dose RSVpreF or placebo. The dose of RSV prefusion F antigen in RSVpreF for this study will be 120 µg (60 µg A and 60 µg B).

Assessments for mothers will include parameters to allow descriptions of safety, tolerability, and immunogenicity of the vaccine in maternal participants.

For all infant participants, data will be collected for any medically attended respiratory illness to assess for cases of LRTI due to RSV (efficacy endpoint). Additionally, throughout the study all respiratory illnesses, SAEs, and NDCMCs reported will be assessed in this population. Infant participants enrolled during the first year of the study will be followed up for 24 months after birth, to include longer-term RTI surveillance and safety oversight to address safety and the possibility of conferred enhanced protection (antibody persistence) during a second RSV season. All other infants will be followed up for 12 months after birth. All MA-RTIs meeting the protocol definition for a potential study endpoint will be adjudicated by an independent EAC. In addition, this study will use an E-DMC to monitor vaccine safety and efficacy and study futility.

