4. ANALYSIS SETS (POPULATIONS FOR ANALYSIS)

Data for all participants will be assessed to determine if participants meet the criteria for inclusion in each analysis population prior to unblinding and releasing the database and classifications will be documented per standard operating procedures.

Population	Description
Enrolled	All participants who sign the informed consent document.
Randomly assigned to investigational product	All maternal participants who are assigned a randomization number in the IRT system.
Evaluable efficacy – infant (per-protocol)	All infant participants who are born to maternal participants who did not have major protocol deviations prior to the delivery and who received the investigational product to which they were randomized at least 14 days prior to delivery, are eligible, and have no major protocol deviations.
ITT efficacy – infant	All infant participants who are born to vaccinated maternal participants.
Evaluable immunogenicity – infant	All infant participants who are born to maternal participants who did not have major protocol deviations prior to the delivery and who received the investigational product to which they were randomized, are eligible, have blood drawn for assay testing within the specified time frame, ^a have valid and determinate assay results for the proposed analysis, and have no major protocol deviations.
Evaluable immunogenicity – maternal	All maternal participants who are eligible, receive the investigational product to which they were randomized, have blood drawn for assay testing within the specified time frame, ^b have valid and determinate assay results for the proposed analysis, and have no major protocol deviations.
ITT immunogenicity – infant	All infant participants who are born to vaccinated maternal participants and have at least 1 valid and determinate assay result for the proposed analysis.
ITT immunogenicity – maternal	All randomized maternal participants who receive investigational product and have at least 1 valid and determinate assay result for the proposed analysis.
Safety – infant	All infant participants who are born to vaccinated maternal participants.
Safety – maternal	All randomized maternal participants who receive investigational product.

- a. A cord blood sample must be obtained on the day of birth. If cord blood is unavailable, a venous blood sample may be collected from the infant preferably within 24 hours but up to 7 days after birth.

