6.3.1.12. IgG Concentrations Against Prefusion F Measured at Birth

- Analysis set: Evaluable immunogenicity – infant ([Section 4](#)).
- Analysis methodology: Descriptive summary statistics. Results obtained from out-of-window blood draws will also be removed. Missing serology results will not be imputed, as MCAR is assumed.
- GMCs of the IgG against prefusion F subgroup A and subgroup B, and combined RSV A/B, at birth will be presented. For each vaccine group, n, GMC, and 95% CI will be presented.

6.3.1.13. MA-RTI, MA-LRTI, and Severe MA-LRTI Due to RSV Occurring 0 to 730 Days After Birth in Premature Infants <37 Weeks of Age

- Analysis set: Evaluable efficacy – infant ([Section 4](#)).
- Analysis methodology: VE will be analyzed using a conditional exact test based on the binomial distribution of the number of disease cases in the RSV vaccine group, given the total number of cases in both groups. Results obtained after the infant received palivizumab or another monoclonal antibody targeting RSV or after he/she had transfusions of more than 20 mL/kg of any blood products at ≤ 180 days of age will be excluded.
- For each group, the number (n), percentage, and 95% CI of MA-RTI, MA-LRTI and severe MA-LRTI due to RSV cases occurring within 0 to 730 days after birth will be presented for each group.
- VE compared to placebo along with the 95% CI will be presented for each analysis interval separately.

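### For windows that open before day 361 and close at day 730, percentages and CIs count infants whose follow-up ends at 12 months as event-free to day 730

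*SAP*

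**What the plan says.** SAP section 2.2 sets two lengths of follow-up: "Infant participants enrolled during the first year of the study will be followed up for 24 months after birth", and "All other infants will be followed up for 12 months after birth".

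Section 6.3.1.2 uses the evaluable efficacy infant set. Section 4 defines that set as "All infant participants who are born to maternal participants who did not have major protocol deviations prior to the delivery", with further conditions on vaccination, eligibility and deviations but none on enrolment year or length of follow-up. On this set, 6.3.1.2 gives the count, percentage and 95% CI of "RSV-positive MA-RTI cases occurring within 181 to 730 days will be presented for each group". The next bullet covers 361 to 730 days and is limited: "just for the participants enrolled in the first year of the study". For VE, the section says only that "VE compared to placebo along with the 95% CI will be presented for each analysis interval separately".

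Sections 6.3.1.3 (all-cause MA-RTI up to day 730) and 6.3.1.5 to 6.3.1.7 (severe MA-LRTI due to RSV, RSV hospitalization and any-cause MA-LRTI, each 181 to 730 days) take their attributes from 6.3.1.2. Section 6.3.1.13, on premature infants, reports "cases occurring within 0 to 730 days after birth will be presented for each group", again without an enrolment-year limit.

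The primary and secondary analyses are fuller. Section 6.2.1.3.1, for example, says of VE: "This will be based on raw numbers of cases and also with an adjustment for any differences in follow-up time", and adds Kaplan-Meier curves.

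**The concern.** In these tables an infant whose planned follow-up ended at 12 months stays in the denominator and cannot contribute a case after that. Such an infant is counted as event-free to day 730. The percentage is then not the incidence over the window named in the table, and its CI is centred on a different quantity.

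The SAP deals with the same problem elsewhere. It limits the 361 to 730 day summary and the 24-month safety analysis (section 6.1.2.4) to first-year infants, and it adjusts primary and secondary VE for follow-up time. The windows at issue have the largest planned difference in follow-up, a full year, and get neither treatment. Section 2.2 gives protection in a second RSV season as part of the reason for 24-month follow-up, so a reader is likely to take a figure to day 730 as bearing on that question.

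**Working it through.** The SAP states no incidence, VE or first-year share for these windows, so there is no planned figure to reproduce. The check is person-time arithmetic.

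**Inputs**
- From sections 2.2 and 6.3.1.2: follow-up to 24 months (taken as day 730) or 12 months (taken as day 360).
- Window lengths: days 181 to 360 are 180 days; days 361 to 730 are 370; days 181 to 730 are 550. The 0 to 730 day window is taken as 730 days, of which 360 are seen in infants followed for 12 months.
- Assumed: share p of infants followed for 24 months = 0.3, 0.5 or 0.7; no dropout; constant hazard unless stated.

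**Share of the window that is observed**
- 181 to 730 days: p + (1 − p) × 180/550 = 0.529, 0.664, 0.798. Unobserved: 47, 34, 20%.
- 0 to 730 days: p + (1 − p) × 360/730 = 0.645, 0.747, 0.848. Unobserved: 35, 25, 15%.

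**Effect on the percentage, rare events**
- Crude percentage = p × (incidence 181–730) + (1 − p) × (incidence 181–360).
- Assume 3% over days 181 to 360. Full follow-up then gives 1 − 0.97^(550/180) = 8.89%.
- p = 0.3: 0.3 × 8.89 + 0.7 × 3 = 4.77%, which is 54% of 8.89%.
- p = 0.5: 0.5 × 8.89 + 0.5 × 3 = 5.94%, which is 67%.
- p = 0.7: 0.7 × 8.89 + 0.3 × 3 = 7.12%, which is 80%.
- The shortfalls of 46, 33 and 20% are close to the unobserved time shares.

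**Effect on the percentage, common events**
- For all-cause MA-RTI over 0 to 730 days, assume 80% have an event by day 730 and p = 0.5.
- Incidence by day 360 is 1 − 0.2^(360/730) = 54.8%. Crude percentage = 0.5 × 80 + 0.5 × 54.8 = 67.4%.
- Shortfall = (80 − 67.4)/80, about 16%, against 25% of time unobserved.

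**Weights behind the 181 to 730 day VE**
- Days 181 to 360 supply 180/(180 + 370p) of observed time: 62, 49 and 41% for p = 0.3, 0.5 and 0.7, against 33% (180/550) with full follow-up.
- The share exceeds one half only if p < 180/370 = 0.486.
- If the later hazard is r times the earlier one, the share of cases is about 180/(180 + 370pr). At p = 0.4 this is 71, 55 and 38% for r = 0.5, 1 and 2.
- Illustration: with VE of 40% in days 181 to 360, 0% afterwards and equal placebo hazards, pooled VE is 0.4 × 180/(180 + 370p), or 25, 20 and 16% for p = 0.3, 0.5 and 0.7, and 13% at p = 1. The vaccine effect is the same in every case; only the enrolment pattern changes.

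**The case against.** The case on the other side has five parts.

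- **Arms are balanced.** Allocation is 1:1, and planned follow-up depends on when the mother enrolled, not on her arm. A reader might infer a biased VE; the SAP does not support that. This stands.
- **Some windows are already handled.** A reader might infer that every window ending at day 730 is affected. The 361 to 730 day summary in 6.3.1.2 is restricted to first-year infants, and 6.3.1.4 inherits that. For MA-LRTI due to RSV, the SAP reports cumulative results to day 360 with follow-up adjustment and 361 to 730 days separately, so the second-season question is addressed for that endpoint. This stands and narrows the point.
- **The inheriting sections may carry the restricted summary too.** Sections 6.3.1.3 and 6.3.1.5 to 6.3.1.7 adopt all attributes of 6.3.1.2, which could include its 361 to 730 day bullet. That is arguable, since each section names a single interval of interest. Even if accepted, it adds a table and leaves the percentage over the longer window unchanged.
- **The denominator could be settled in table shells**, which section 2 says are prepared separately. Possibly so, but the SAP names the analysis set and states no other denominator for these windows.
- **The size is assumed.** It rests on an unstated first-year share and a constant hazard, while section 2.2 describes seasonal RSV over several seasons. This stands; the direction is firmer than the amount.

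**Conclusion.** The point holds for the first interval of 6.3.1.2, for 6.3.1.3, 6.3.1.5 to 6.3.1.7 and 6.3.1.13. Read as written, their percentages understate incidence over the stated window whenever some infants are followed for only 12 months and events occur after that. With rare events, a constant hazard and 30 to 70% of infants followed for 24 months, the understatement is roughly 47 to 20% for 181 to 730 days and 35 to 15% for 0 to 730 days. It is less for common events such as all-cause MA-RTI.

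The VE is a fair comparison between arms, but it averages two periods with weights set by enrolment timing. A reader might go further and say that it mostly reflects days 181 to 360. That needs a first-year share below about 0.49 at equal hazards, and the SAP gives neither the share nor the hazards. What can be said is that the weighting leans towards the earlier period compared with full follow-up.

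These endpoints are exploratory and lie outside the alpha-controlled testing, so no trial decision depends on them. The point is minor, but it concerns a reported quantity that does not match its label.

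**What to change.** For the listed windows, report cases per person-time at risk, or Kaplan-Meier incidence, and give a follow-up-adjusted VE as the primary and secondary analyses already do. Alternatively, restrict these windows to infants of first-year enrollees, as 6.3.1.2 does for 361 to 730 days. In either case, show 181 to 360 days in all infants and 361 to 730 days in first-year infants as separate results.

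The cost is a person-time denominator or a population flag in existing exploratory tables. Restriction also discards observed events from later enrollees. That loss matters most in the premature subgroup of 6.3.1.13, where person-time is the better choice.

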6.3.1.3. Incidence of All-Cause MA-RTIs Up to 730 Days After Birth

The interval of interest for this analysis is up to 730 days after birth. All attributes (including analysis methodology and reporting results) for this endpoint will be similar to those stated in Section 6.3.1.2.

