3.3. Other Endpoints

3.3.1. Exploratory Endpoints – Infant Participants

- RSV-positive MA-RTI (as confirmed by the EAC) occurring within 90 days, 120 days, 150 days, and 180 days after birth.
- RSV-positive MA-RTI occurring 181 to 730 days after birth.
- Incidence of all-cause MA-RTIs up to 730 days after birth.
- MA-LRTIs due to RSV occurring 361 to 730 days after birth.

- Severe MA-LRTIs due to RSV occurring 181 to 730 days after birth (as confirmed by the EAC).
- Hospitalization due to RSV occurring 181 to 730 days after birth (as confirmed by the EAC).
- MA-LRTIs due to any cause occurring 181 to 730 days after birth.
- RSV subgroup A– and subgroup B–specific MA-LRTI.
- Positivity for non-RSV respiratory pathogens obtained at unplanned MA-RTI visits.
- RSV A and RSV B serum neutralizing titers measured at birth.
- Primary and secondary efficacy by select demographic risk factors (eg, breastfeeding, maternal smoking, number of household members).
- Univariate summaries of healthcare utilization variables, which may include the following: number and type of medical visits, length of hospital stay, requirement for mechanical ventilation, requirement for respiratory diagnostic procedures, requirement for IV fluids, requirement for prescriptions, and antibiotic use.
- IgG concentrations against prefusion F measured at birth.
- MA-RTI, MA-LRTI, and severe MA-LRTI due to RSV occurring 0 to 730 days after birth in premature infants <37 weeks of age.

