5.2.1. Analyses for Binary Endpoints

The number and percentage of participants in each category will be summarized. The 95% CI for percentage, and for the difference in percentages, will also be presented, where appropriate.

The analysis of efficacy will use a conditional exact test¹ based on the binomial distribution of the number of disease cases in the RSV vaccine group, given the total number of cases in both groups. The number of cases $x_i \sim P(\lambda_i)$, where $P()$ is the Poisson distribution ($i = 1$ denotes placebo, $i = 2$ denotes vaccine). It is known that $x_2|T = t \sim B(T, \pi)$, where $B()$ is the binomial distribution, $T = x_1 + x_2$ (the total number of events), and $\pi = \lambda_2 / (\lambda_1 + \lambda_2)$. Then, assuming equal numbers of participants per group, testing the hypothesis $H_0: VE \leq \theta$ is equivalent to testing $H_0: \pi \geq (1 - \theta) / (2 - \theta)$.

The 95% CI for proportions will be constructed by the Clopper-Pearson method described by Newcombe.² The 95% CI will be presented in terms of percentage.

The 95% CI for differences in the proportions will be computed using the Miettinen and Nurminen method.³ The 95% CI will be presented in terms of percentage.

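### SAP 6.3.1.3 analyses recurrent all-cause MA-RTI with a conditional exact test but never fixes the counting unit, and the test suits neither possible unit

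*SAP*

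**What the plan says.** SAP Section 3.3.1 lists the endpoint as "Incidence of all-cause MA-RTIs up to 730 days after birth". The matching objective in Section 2.1.3.1 is efficacy in reducing the incidence of MA-RTI.

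Section 6.3.1.3 states the interval and refers everything else elsewhere: "All attributes (including analysis methodology and reporting results) for this endpoint will be similar to those stated in Section 6.3.1.2". Section 6.3.1.2 concerns RSV-positive MA-RTI. Its method is: "VE will be analyzed using a conditional exact test based on the binomial distribution of the number of disease cases in the RSV vaccine group". Its reporting is "the number (n), percentage, and 95% CI of RSV-positive MA-RTI cases occurring within 181 to 730 days will be presented for each group", followed by "VE compared to placebo along with the 95% CI will be presented for each analysis interval separately".

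The test is set out in Section 5.2.1, under the heading for binary endpoints. That section opens with "The number and percentage of participants in each category will be summarized". It then models the case count in each group as Poisson and conditions on the total ("Then, assuming equal numbers of participants per group, testing the hypothesis").

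Table 8 defines an infant MA-RTI visit broadly: a medically attended visit plus any one of several signs, among them cough, nasal discharge lasting at least 24 hours, or another respiratory symptom of concern. Section 2.2 gives 24 months of follow-up to infants enrolled in the first year and 12 months to all others.

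**The concern.** An all-cause MA-RTI can happen several times to one infant over one or two years. A method written for RSV-positive illness has been carried over without saying what one case is. Two readings are open.

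- **Each infant counts once.** The percentage and the binary-endpoints heading point this way. Second and later illnesses then have no effect on VE. As the share of infants with at least one illness rises, the two percentages converge and the risk-ratio VE moves toward 0. The conditional test also uses a Poisson variance, which is too large for a common yes/no outcome.
- **Every episode counts.** Episodes within an infant are correlated, so the totals vary more than Poisson counts and the interval is too narrow.

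In addition, Section 6.3.1.2 lacks the adjustment for follow-up time that Sections 6.1.1.1.1, 6.2.1.1.1 and 6.2.1.3.1 include, so 6.3.1.3 does not inherit one although follow-up is mixed.

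At stake is an exploratory VE with a 95% CI. It could come out near 0 and be misread as no effect on respiratory illness burden, or carry an interval that looks more precise than it is.

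**Working it through.** **1. Test checked on the plan's own figures.** The SAP gives no rate, effect or power for this endpoint, so the same exact test was checked against Table 11. The Clopper-Pearson limits for the vaccine share π were converted by VE = 1 − π/(1 − π).
- 6 of 43 cases at half of 0.014% one-sided: VE 83.8% (27.2%, 98.3%). Table 11 has 84% (27%, 98%).
- 14 of 62 cases at half of 0.15% one-sided: 70.8% (25.4%, 90.5%). Table 11 has 71% (25%, 91%).

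The 29-of-62 row also agrees. The lower limit for 24 of 43 comes out at −143.9% against the printed −145%, which has no bearing here.

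**2. Inputs.**
- From the SAP: 1:1 allocation and about 6900 pairs (Section 2.2), so n = 6900/2 = 3450 per group; 95% CI (Section 6.3.1.2).
- Assumed: mean μ = 0.5 to 3 episodes per placebo infant over actual follow-up; gamma-Poisson counts with variance μ + φμ², φ = 0.3 to 1.0; true rate reduction 10%. The 12/24-month mix is not modelled.

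**3. Formulas.**
- Share with at least one illness: p = 1 − (1 + φμ)^(−1/φ). Cases per group: x = np.
- Planned test (Poisson variance): SE(log RR) = √(1/x0 + 1/x1).
- Correct binomial: SE = √((1 − p0)/x0 + (1 − p1)/x1). This is also the true SD of log RR.
- Episode rate: SE = √((1/μ0 + φ)/n + (1/μ1 + φ)/n), with log rate ratio ln(0.9) = −0.1054.
- Power of the planned test: Φ((|log RR| − 1.96·SE_planned)/SE_binomial). The other two: Φ(|effect|/SE − 1.96).

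**4. Power with φ = 0.5 and a 10% reduction.**

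| | μ = 0.5 | μ = 2 |
|---|---|---|
| p0, p1 | 36.0%, 33.4% | 75.0%, 72.3% |
| VE on any-versus-none | 7.3% | 3.6% |
| \|log RR\| | 0.0761 | 0.0367 |
| SE planned / binomial | 0.0409 / 0.0331 | 0.0281 / 0.0144 |
| SE episode rate | 0.0389 | 0.0244 |
| Power, planned test | 45% | 10% |
| Power, correct binomial test | 63% | 72% |
| Power, episode rate | 77% | 99% |

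Simulating the exact test itself (4000 runs) gave 43.6% and 10.0% for the planned test, so the approximation is adequate.

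**5. Splitting the loss.** The step from episode rate to correct binomial is the cost of dichotomising: 77 − 63 = 14 points at μ = 0.5 and 99 − 72 = 27 points at μ = 2. The step from correct binomial to planned is the cost of the conditional test: 63 − 45 = 18 points and 72 − 10 = 62 points.

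**6. Actual level of a nominal two-sided 5% test with no effect.**
- One case per infant: 2·P(Z > 1.96/√(1 − p)). At μ = 0.5, φ = 1, p = 0.333 and the level is 1.6%. At μ = 3, φ = 0.3, p = 0.882 and it is practically 0%.
- All episodes: 2·P(Z > 1.96/√(1 + φμ)). At μ = 0.5, φ = 0.3 it is 2·P(Z > 1.96/√1.15) = 7%. At μ = 3, φ = 1 it is 2·P(Z > 1.96/√4) = 33%.

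Simulation of the exact test on all episodes, at one-sided 2.5% with φ = 0.5 to 1, gave about 4% to 16%, in line with this.

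**The case against.** **The plan never says any-versus-none.** Correct. A reader might infer that the SAP reduces the endpoint to one case per infant. The percentage and the binary-endpoints heading make that likely, but no sentence states it. The point therefore rests on the unfixed counting unit and on the test failing under both readings.

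**Most of the power is lost.** This too is tempting but not supported without conditions. The SAP gives no MA-RTI rate. At a mean of 0.5 episodes the planned test keeps 45% power against 77%, and much of the gap comes from the Poisson-based test, not from leaving out repeats. A collapse needs roughly 1 to 2 or more episodes per infant.

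**Repeat visits are not dropped from the plan.** Partly right. Section 3.6.1 collects healthcare use at each MA-RTI visit, and Section 6.3.1.11.1 compares the number of medical visits between groups. But that is a raw difference in means in the safety population, with no VE and no allowance for follow-up time. It does not answer the efficacy objective.

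**The endpoint is exploratory, and risk-ratio VE is the SAP's scale throughout.** Both are true. No alpha or power target is attached here, and a rate-ratio VE would not be directly comparable with the first-event VEs. This limits the severity but does not repair the interval.

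**Conclusion.** The point holds in a limited form. Section 6.3.1.3 does not fix what counts as a case, and the inherited conditional exact test is miscalibrated for a common, recurrent outcome under either reading. Counted once per infant, the nominal two-sided 5% level is about 0% to 1.6% and VE is drawn toward 0. With all episodes counted, it is about 7% to 33%. With 3450 per group, dispersion 0.5 and a 10% rate reduction, the planned test has about 45% power against 77% for a rate model at a mean of 0.5 episodes, and 10% against 99% at a mean of 2. Part of each gap is due to the test and part to dichotomising.

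All of these sizes rest on assumed episode rates, dispersion and effect, because the SAP states none for this endpoint. Severity is low: the endpoint is exploratory and no trial decision depends on it.

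**What to change.** In Section 6.3.1.3, replace the cross-reference for the VE analysis with the following:
- All MA-RTI episodes per infant count. A prespecified rule decides when a later visit is a new episode, with its interval in days fixed before unblinding.
- VE = 100 × (1 − rate ratio) with 95% CI, from a negative binomial model, or a Poisson model with robust variance clustered by infant. Vaccine group is the factor and log follow-up time the offset, since follow-up is 12 or 24 months.
- The number and percentage of infants with at least one MA-RTI stay as a descriptive summary.
- A footnote says that this VE is based on a rate ratio, not a first-event risk ratio.

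The cost is a short SAP edit, one added model and one episode rule, using visit data already collected. The drawback is that this VE is on a different scale from the others, which the footnote covers.
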